activity, such that a high LDAEP reflects low serotonergic neurotransmission (Hegerl et al 1998; Juckel et al 1999; Strobel et al 2003). It is thought that the neural generator of the LDAEP is the primary auditory cortex (Juckel et al 1997), which is a region that has a high concentration of serotonin (Azmitia & Ganno, 1986; Lewis et al 1986). In LDAEP studies, participants listen to an increasing sound intensity (usually between 60-100 dB) and the amplitude of specific ERP components (e.g. N1 and P2) should increase with each intensity increase. Although few studies have found significant effects of depression on the LDAEP (Brocke et al 2000), many have found increased LDAEP in responders to selective serotonin reuptake inhibitor (SSRI) treatment (Paige et al 1994; Linka et al 2004; Lee et al 2005; Mulert et al 2007). Interestingly, one study found that depressed patients with a high LDAEP did not respond to a norepinephrine reuptake inhibitor (NRI; Linka et al 2005). These studies support the notion that LDAEP may be sensitive to serotonergic changes that may result in psychopathological conditions that are thought to involve deficiencies in serotonin, such as depression. By including the LDAEP task in this proposal, we can 1) examine the relationship between the LDAEP (as a proxy of serotonergic neurotransmission) and 5-HT1A receptor binding (as measured by our PET scan using the CUMI tracer), and 2) examine if baseline LDAEP level is predictive of lamictal or lithium treatment response.

C. Preliminary Studies C.1. 5-HTT Binding in Bipolar Disorder:

Prior to the use of [11C]McN5652 in populations we carefully evaluated the ligand to determine the optimal data acquisition and analysis methods.⁷ Demographics of the 18 subjects (10 female, 8 male) who met DSM-IV(1994) criteria for bipolar disorder with a major depressive (MDE) and 41 healthy episode volunteers (19 female, 22 male) who participated in this study are presented Table 1. Inclusion and exclusion criteria were evaluated by clinical history, chart review. Structured Clinical Interview for DSM IV (SCID I)¹³³, Hamilton Depression Rating Scale for depression (HAM-D)¹³⁴, review of systems, physical examination, routine blood tests, pregnancy test, and urine toxicology. The healthy volunteer group was free of lifetime psychiatric history and had no first-degree relatives with mood disorders.

in Bipolar Table 1. Demographics of the [11C]McN5652 Bipolar Study Groups

U 1		•			1
	Healthy	Depressed			

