Study criteria for healthy volunteers were similar except for the absence of a psychiatric history, including alcohol and substance abuse and absence of mood or psychotic disorder in their first-degree relatives. The Institutional Review **Boards** Columbia of University Presbyterian Hospital and the New York State Psychiatric Institute approved the protocol. Subjects gave written informed consent after detailed explanation of the study.

Healthy volunteer and bipolar disorder groups were matched for age (range 18 to 65 vears; t =0 .35, p = 0.73) and sex (γ^2 = 0.43, p = 0.51). Eight bipolar subjects met the criteria for Bipolar II disorder, 10 met criteria for Bipolar I disorder. Other Axis I disorders included Binge Eating (2), Obsessive-Compulsive Disorder (3), Simple Phobia (1), Generalized Anxiety Disorder (1), Post-Traumatic Stress Disorder (PTSD, 2). Nine bipolar subjects had made suicide attempts

 $(2.33 \pm 1.87 \text{ lifetime attempts, range 1 - 7})$. Bipolar subjects averaged 23.72 \pm 6.27 on the Hamilton depression rating scale (24 item), while the healthy volunteer group averaged 0.61 ± 0.89 . Data from this healthy volunteer sample was reported in a previous study involving Major Depressive Disorder.⁹ The injected dose of [11C]McN5652 injected was not different between healthy volunteers (11.89 \pm 4.10 mCi) and bipolar subjects $(12.79 \pm 4.85 \text{ mCi}, \text{ Students' t} = -0.733, p = 0.466)$. Specific activity (healthy volunteers = 0.97 ± 0.69 mCi/nmol, bipolar = 0.81 ± 0.40 mCi/nmol, Students' t = 0.921, p = 0.361) and injected mass (healthy volunteers = 70.45 ± 69.10 µmole, bipolar = 50.40 ± 23.22 µmole, Students' t = 1.20, p = 0.236) also did not differ.

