All patients will be assessed clinically through history, chart review, Structured Clinical Interview for DSM IV (SCID I)¹³³, review of systems, physical examination, routine blood tests, pregnancy test, urine toxicology and electrocardiogram. The Beck Depression Inventory (BDI)¹⁵⁵, Hamilton Depression Rating Scale (HDRS)¹³⁴, and Global Assessment Scale¹⁵⁶ will be used to assess subjective and objective depression severity and functional impairment, respectively. Patients who currently meet criteria for bipolar disorder, as assessed by the Structured Clinical Interview for DSM-IV (SCID I), and who have a 17-Item HDRS score of at least 15 or a 17-Item HDRS score of 10 to 14 in conjunction with a BDI score of at least 29 will be recruited for this study. Patients who currently meet criteria unipolar depression and are in a current major depressive episode, as assessed by the Structured Clinical Interview for DSM-IV (SCID I), and who have a 17-Item HDRS score of at least 15 or a 17-Item HDRS score of 10 to 14 in conjunction with a BDI score of at least 29 will be recruited for this study.

Patients with prior antidepressant treatment will undergo a three-week medication washout prior to enrollment in the study. Although this is a relatively prolonged washout, we have shown that depressed patients who are washed out of antidepressants that they had failed to respond to do not worsen, rather report modest improvement in their symptoms. 159

Normal controls are recruited to provide normative values on the clinical and brain imaging measures used. Subjects are screened for mental and physical health. Family history of psychiatric disorder is assessed using the Family Interview for Genetic Studies (FIGS). Urinary drug screen, physical examination and laboratory testing are performed prior to acceptance as a control subject. The normal control sample is selected to match the mean, variance and shape of the distributions across the clinical sample, at a group level. Matching variables are age, gender, socioeconomic status, education, marital and employment status, and race.

BIPOLAR PATIENTS:

INCLUSION:	
(1) Patients diagnosed with bipolar disorder. Patients on	As defined by the DSM-IV by
psychiatric medication will have failed their current	means of the SCID
regimen for the treatment of their depression: they	
will meet criteria for depression, be seeking	
treatment for it, and have been on an adequate dose	
of antidepressant or mood stabilizer (as defined by	

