 (8) Current, past or anticipated exposure to radiation, that may include: being badged for radiation exposure in the workplace participation in nuclear medicine procedures, including research protocols in the last year.* (9) A neurological disease or loss of consciousness for 	1. Subjects will undergo a clinical interview, during which they will be asked whether or not they have worked with radioactive substances or have been badged in the past. In addition, they are asked about any prior chemotherapy or radiation treatment. 2. A research assistant will check our database to ensure that the subject has not participated in an imaging study within our department in the past year. Clinical interview
more than a few minutes (10) Medicinal patch that cannot be removed**	Medical history (by a physician),
(11)Patients who are responding satisfactorily to psychiatric medications, because they will not be washed-out for purposes of this study	physical exam. History
(12) A documented history of a lack of response to a trial of adequate dose and duration of both lithium and lamotrigine defined as minimal clinical response to lamotrigine 200 mgs for at least 4 weeks or lithium serum levels of at least 0.8 (or dose >= 900 mgs) for at least 4 weeks	History
(13) Patient is unlikely to be able to tolerate medication washout	Clinical interview
(14) Claustrophobia	Clinical interview

Approved: 12/13/2019
Expiration Date: 12/12/2020
Stony Brook University Human Subjects Committee (IRB)
PSF 2/23/15

Page 12 of 37

IRB# 2012-1826-F PI: [name]

(15) Blood donation within 8 weeks of the start of the study.	Clinical interview
(16) History of a bleeding disorder or are currently taking anticoagulants (such as Coumadin, Heparin, Pradaxa, Xarelto).	History

^{*} Subjects will be eligible if the injected dose and dosimetry of the radiotracer are known and the cumulative annual exposure of the previous study and this study is lower than the annual limit for research subjects defined by the FDA (see below)

HEALTHY VOLUNTEERS:

INCLUSION:		
(1) No lifetime history of Axis I disorders other than	Structured Clinical Interviews I	
specific phobia, social phobia, and/or adjustment	for DSM IV; clinical history and	
disorder.	interview	
(2) Age range 18-70 years.	Interview	
(3) Willing to travel to Yale University for PET	Interview	
scanning.		
EXCLUSION:		
(1) Past or present alcohol/substance abuse or	SCID; Urine drug screen	
dependence except for cannabis use disorders,		

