which are not exclusionary; IV drug use in the		
past 5 years; IV drug use in the past 5 years or		
ecstasy (MDMA) use more than 15 times in the		
past 10 years or any MDMA use in the past		
month.		
(2) A first-degree relative with history of major	Clinical interview, Family	
depression if participant is less than 44 years old	Interview for Genetic Studies	
(median age of onset plus one quartile) ¹⁷⁴ ,	(FIGS)	
schizophrenia, schizoaffective disorder, or suicide		
attempt; two or more first degree relatives with a		
history of substance dependence if the participant		
is less than 27 years old (median age of onset plus		
one quartile). ¹⁷⁴ .		
(3) Significant active physical illness particularly	Medical history (by a physician),	
those that may affect the brain or serotonergic	physical exam, screening lab	
system including blood dyscrasias lymphomas,	tests (comprehensive metabolic	
hypersplenism, endocrinopathies, renal failure or	panel, CBC with differential,	
chronic obstructive lung disease, autonomic	thyroid function tests [TSH and	
neuropathies, peripheral vascular disease,	free T4], PT/PTT, urine test for	
diabetes, low hemoglobin and malignancy, significant anemic disease or blood loss, and the	pregnancy, and urine drug	
following lab parameters:	screen) (approximately 15.2 ml of blood drawn). A physician	
Toffowing fau parameters.	will review lab findings to ensure	
platelet count < 80,000	that there are no anemia related	
	a mat there are no anemia related	

^{**} In case the subject does have a medicinal patch, they will be asked to remove it prior to the MRI scan session

Page 13 of 37

IRB# 2012-1826-F PI: [name]

	contraindications to participation.
(4) Lacks capacity to consent	Clinical interview
(5) Pregnancy, currently lactating; planning to conceive during the course of study participation or abortion in the past two months	HCG pregnancy test to rule out pregnancy or unwilling/unable to use a medically acceptable means of birth control through the course of the study. Urine pregnancy test will be done at screening. A urine pregnancy test will be done on the day of the PET scan prior to scanning. In addition, each female subject must confirm that she is using an acceptable method of birth control for at least two weeks prior to the PET scan.
(6) Metal implants, pacemaker or metal prostheses or orthodontic appliances, the presence of shrapnel	History

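### The healthy-volunteer family-history exclusion does not name bipolar disorder, so some controls with a bipolar first-degree relative are eligible as written; the likely effect on Aim 1 is modest

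*Protocol*

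**What the plan says.** Protocol section D.4, Healthy Volunteers, exclusion 2 has four parts:

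- Major depression in a relative: it opens "A first-degree relative with history of major" and continues with an age condition, "depression if participant is less than 44 years old".
- Three items with no age condition of their own: "schizophrenia, schizoaffective disorder, or suicide" attempt.
- A substance-dependence item, "attempt; two or more first degree relatives with a" history of it, applied only to participants under 27.
- The Family Interview for Genetic Studies (FIGS), listed with the clinical interview as the means of assessment.

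Bipolar disorder in a relative appears neither here nor in any other healthy-volunteer criterion. Inclusion 1, "No lifetime history of Axis I disorders other than" a few named conditions, concerns the volunteer's own history. The Screening text says "Family history of psychiatric disorder is assessed using the Family Interview for Genetic Studies (FIGS"), but attaches no exclusion rule to the result.

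The preliminary studies used a broader rule. In section C.1 the healthy volunteers "had no first-degree relatives with mood disorders", restated as "absence of mood or psychotic disorder in their first-degree relatives". Section C.2 applies the same rule to the 5-HT1A controls. Section E, Power Analyses, takes the diagnosis effect for the sample size from the preliminary 5-HTT data in bipolar disorder.

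**The concern.** The family history closest to the disease under study is the one the exclusion does not mention. Major depression is not a dependable substitute. Table 1 in section C.1 records relatives with MDD and relatives with BD on separate rows, so the investigators treat them as different histories, and the depression item lapses at age 44 while controls may be up to 70.

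The sample size therefore rests on a contrast with controls free of familial mood disorder, while the study may enrol controls who are not. Section C.1 leaves open whether low 5-HTT binding is a trait or occurs only in the depressed state. If it were partly a familial trait, controls with a bipolar relative would pull the control mean toward the patients. That would shrink the Aim 1 difference and shift the reference used in SAP Question 1, where pre- and post-treatment patients are set against healthy controls. The protocol gives no reason for the change from its preliminary rule.

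**Working it through.** **1. Who is eligible as written.** Take a volunteer with one bipolar first-degree relative and no other relevant history.

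| Volunteer | Relative attempted suicide | Relative did not |
|---|---|---|
| Under 44 | Excluded | Excluded only if the relative's depressive episodes are read as major depression |
| 44 to 70 | Excluded | Eligible |

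**2. The plan's own figure.** Section E states 80% power with 38 bipolar subjects and 38 controls, from a mixed-model simulation whose variance inputs are not given. A two-group approximation uses F = 5.41 with 18 bipolar subjects and 41 controls (section C.1):

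d = √[F × (1/18 + 1/41)] = √[5.41 × (1/18 + 1/41)] = 0.658.

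With 38 per group and two-sided α = 0.05 (assumed; the power section states none), the noncentrality is 0.658 × √(38/2) = 2.87. The noncentral t on 74 df gives power of 80.8%, which agrees with the stated 80%.

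**3. How many controls might be affected.** Let q be the probability of at least one bipolar first-degree relative: q = 1 − (1 − prevalence)^k.

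- Prevalence: 1% to 2%. The protocol gives this as a one-year rate; using it for a relative's history is an assumption.
- k: 3 to 6 first-degree relatives, treated as independent (assumed).
- Low end: 1 − 0.99³ = 0.030, or 1.1 of 38.
- High end: 1 − 0.98⁶ = 0.114, or 4.3 of 38.

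Some of these volunteers are already excluded by the suicide-attempt item. Table 1 shows previous attempts in 9 of 18 bipolar patients (50%). Applying 50% to relatives (assumed) leaves 0.6 to 2.2 of 38. Nothing is deducted for the under-44 depression item.

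**4. Effect on power.** If affected controls carry a fraction g of the deficit, the expected difference becomes d × (1 − q × g), where q is the share still eligible. Only g = 1 and g = 0.5 are shown; the documents give no value.

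| Already excluded | Share q of controls | Power, g = 1 | Power, g = 0.5 |
|---|---|---|---|
| Half | 0.015 to 0.057 | 79.6% to 76.0% | 80.2% to 78.5% |
| None | 0.030 to 0.114 | 78.4% to 70.8% | 79.6% to 76.0% |

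For example, q = 0.057 and g = 1 give d = 0.658 × 0.943 = 0.620 and power of 76.0%. The lowest figure, 70.8%, needs 2% prevalence, six relatives, nobody already excluded and full sharing all at once.

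**The case against.** The strongest reply is that the existing items already catch many of these volunteers. A relative's suicide attempt excludes at any age. The protocol describes bipolar disorder as including recurrent major depressive episodes, so a screener could fairly apply the depression item to controls under 44, and the preliminary controls averaged 38.1 years. Staff may also turn such volunteers away after the FIGS. This stands as an argument about size, and the main illustration allows for the suicide-attempt route. It does not close the gap: the depression route ends at 44, and no written rule requires exclusion on the FIGS result.

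A second reply is that shared deficit in relatives is speculative. That also stands. Section C.1 raises trait against state for patients only, and no passage says that unaffected relatives have low binding. These controls must themselves be almost free of lifetime Axis I disorder.

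Third, the inputs are weak, and in both directions. A one-year rate may understate how many relatives have a history of the illness, while treating relatives as independent overstates how many volunteers have at least one when illness clusters in families.

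Two stronger readings are tempting. A reader might infer that any volunteer with a bipolar parent or sibling is eligible; the indirect routes show otherwise. A reader might also infer that the Aim 2 lithium analysis is compromised. Its power is stated for a paired pre/post analysis, and healthy volunteers have no follow-up PET scans, so only the comparison with controls is exposed.

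**Conclusion.** The omission is clear on the text: bipolar disorder in a first-degree relative is not an exclusion for controls, and this departs, without explanation, from the control definition behind the planning effect. The consequence is modest and rests on assumptions. With half of such volunteers already excluded, power is about 80% to 76% at full sharing and 80% to 78% at half sharing, against 81% without dilution; 71% is an extreme rather than an expectation. The documents fix neither the share of controls affected nor the extent to which they would carry the deficit.

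Any such bias runs toward no difference in Aim 1 and in the SAP comparison with healthy controls, so it would not create a false deficit. The documents do not support a claim that the control group is materially contaminated. They do support correcting the criterion, because the plan has almost no margin above 80% and the correction is cheap.

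**What to change.** Add bipolar disorder to the first-degree-relative conditions in healthy-volunteer exclusion 2, and reconcile that criterion with the preliminary-study definition, which excluded any mood disorder in a first-degree relative. If the under-44 limit on major depression is kept, give the reason for departing from that definition; adding bipolar disorder alone does not restore it.

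For controls already scanned, use the FIGS to flag any first-degree relative with bipolar disorder and, for controls aged 44 or over, any with major depression. Report Aim 1 and SAP Question 1 with and without the flagged controls. No scan is discarded, and this can be done even if recruitment has finished.

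The cost is a short amendment to the eligibility table, a few screened controls lost and one extra sensitivity analysis. The interview is already part of screening. If staff already exclude these volunteers in practice, the amendment simply documents it.

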All subjects will have a complete medical history and clinical examination to exclude significant physical illness as described above. Approximately 15.2 ml of blood will be drawn at the screening visit for laboratory testing. A urine sample will also be collected. The following tests will be performed before the study: 1) clinical blood count including differential; 2) metabolic panel (14) comprehensive (Alanine aminotransferase (ALT/SGPT); albumin:globulin (A:G) ratio; albumin, serum; alkaline phosphatase, serum; aspartate aminotransferase (AST/SGOT); bilirubin, total; BUN; BUN:creatinine ratio; calcium, serum; carbon dioxide, total; chloride, serum; creatinine, serum; globulin, total; glucose, serum; potassium, serum; protein, total, serum; sodium, serum); 3) thyroid function tests (TSH and free T4) 4) PT/PTT 5) drug screen; 6) and pregnancy test. Other tests will be performed if there are specific indications.

5. Procedures

Collection of Genetic Information

Stony Brook University Human Subjects Committee (IRB)
PSF 2/23/15

PSF 2/23/15 Page 17 of 37

IRB# 2012-1826-F PI: [name]

Whole blood (approximately 8 ml) will be drawn for assays of candidate gene expression and polymorphisms (i.e., genetic polymorphism of tryptophan hydroxylase, serotonin transporter, etc.).

MRI Scan

An MRI scan will be performed to localize anatomic regions of interest on the PET scan. MRI scans will be performed at the Stony Brook University SCAN Center. Participants will receive an array of structural and functional MRI scans (e.g. T1 and T2-weighted structural images, diffusion tensor imaging [DTI], pseudocontinuous arterial spin labeling [pCASL], etc.) over the course of approximately 1 to 1.5 hours. Patients will be monitored by the MRI technician and research assistant, who will be available at all times. A study physician will also be available if it is necessary. The procedure will be immediately stopped if subjects exhibit significant distress.

Repeat MRI: patient participants will have a second MRI scan following their treatment period (scheduled approximately one week before or after the second set of PET scans). Control participants will be asked to return for a second MRI approximately 12 weeks after their initial MRI. This is optional for control participants.

PET Studies

Approximately 8ml of blood will be drawn the day of the PET scans for female participants to assess their stage in the menstrual cycle.

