PET experiments will be conducted at the Yale University PET Center, [name], in New Haven, CT. [11C]CUMI-101 and [11C]DASB scans will be performed. Participants may have only one of these scans, depending on radiotracer availability. The PET scans will preferably be performed after the MRI scan, but the order may be reversed if needed.

Participants will be provided with transportation from Stony Brook University to Yale University by a combination of taxi/car service, ferry, and/or train. Participants will be accompanied by a staff member while traveling to/from Yale University. Participants will arrive the night before the scheduled scan day(s) and be given accommodations at a nearby hotel at no cost to them.

On the day of the scans, a urine pregnancy test will be done on females to ensure that pregnancy has not occurred between the time of the screening and the PET scans. All participants will also have a urine drug screen. The preparation of the subject will include the placement of one venous lines (for radiotracer injection), a second venous line (for and blood sampling), and an arterial line (for blood sampling). An experienced physician will place the arterial line after infiltration of the skin with 1% lidocaine. A transmission scan is then obtained. Before injection of the radiotracer, approximately 8ml of venous blood will be collected. For the [¹¹C]CUMI-101 scan, up to 20 mCi of [¹¹C]CUMI-101 (mass dose of 5 µg or less) will be administered i.v. after the transmission scan. Emission data will be collected for up to 120 minutes. At the time of injection, arterial sampling will be initiated. In order to demonstrate that the arterial and venous metabolites are the same for late time points, a 4 mL venous sample will be initiated at 60 and 90 minutes. 90 ml or less will be collected during scan time.

At the end of the scan, subjects will be provided with a light meal and be allowed to relax. For the [\frac{11}{C}]DASB scan, the subject will go back on the scanner table and an injection of up to 20 mCi of [\frac{11}{C}]DASB, (mass dose of 10 \mug or less) will be administered. Emission scan and arterial sampling will be resumed as described above. A 4 mL venous sample will be initiated at 50 and 80 minutes. Thus, maximal blood sampling during the entire PET procedure will be approximately 180 ml (about 12 tablespoons).

IRB# 2012-1826-F PI: [name] Stony Brook University Human Subjects Committee (IRB) PSF 2/23/15

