PSF 2/23/15 Page 18 of 37

The order of [\(^{11}\)C]CUMI-101 and [\(^{11}\)C]DASB administration may be reversed, or subjects may participate in only one scan (either [\(^{11}\)C]CUMI-101 or [\(^{11}\)C]DASB),.

In cases where the subject has a hemoglobin level less than 12 for males and less than 11 for females, we would forgo blood drawing for the [11C]DASB scan except for one sample to be taken at the 50 minute time point, as outlined in the simultaneous estimation (SIME) approach. Likewise, we would forego blood drawing for the [11C]CUMI-101 scan except for one sample at the 60 minute time point. We have recently confirmed that this provides an excellent estimate of the plasma parameters necessary for quantification and modeling of this radioligand. It involves drawing one 12 cc sample off the arterial line at the 50 min post-radioligand injection time point. Therefore, instead of 120 cc being drawn during the DASB scan, we would reduce the blood drawn to 12 cc.

In the case that the two injections are planned but cannot be done on the same day once the PET procedures have been started, subjects may be asked to return on a separate day in order to complete the scans. If the PET procedure has to be rescheduled and placement of another aline is required, subject consent will be sought.

After the acute treatment period, the patients who are on either lithium or lamotrigine will have a second PET scanning session that is identical to the first: up to 20 mCi or less of [11C]CUMI-101 and up to 20 mCi of [11C]DASB. Healthy volunteers will not have follow up scans.

Alternate Location and Tracer for PET Scans

Due to limited availability of PET scans at the Yale PET center, alternative arrangements will be made for subjects at Stony Brook Medicine. In cases where the subject cannot accommodate a trip to the Yale PET center or the Yale PET center cannot accommodate for enough scans due to decreased scan staff, PET/MRI scans may take place at the Siemens Biograph mMR-System located at the Ambulatory Imaging Center using [18F]MeFWAY. Similar to the [11C]CUMI-101 scans being performed at the Yale PET center, [18F]MeFWAY also has the capability to examine 5-HT_{1A} binding. Only bipolar and unipolar patients will be scanned at Stony Brook, when Yale is unable to accommodate the number of scans necessary. Healthy controls will continue to be scanned at Yale PET Center.

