Participants will complete a metal screening form prior to procedure to ensure there are no MRI contraindications (e.g. pacemaker, non-MR safe metal implants). A pregnancy test will be performed on the day of the scan for female participants to confirm that pregnancy has not occurred. And we will also measure female hormones by blood samples to ensure if contraceptives were used and if not, the results of the hormone levels can be used as covariates for the data analysis. Preparation of the subject will include the placement of venous lines (for radiotracer injection and blood sampling), and an arterial line (for blood sampling only). At the time of injection, blood sampling will be initiated. 120 mL or less (about 4 ounces or 1/2 cup) will be collected during each scan. The wrist scanner will also be placed around the subject's wrist.

Participants will be asked to urinate in a cup to determine the validity of the dosimetry for future studies.

Bolus Protocol: For each scan, participants will receive a venous injection (bolus delivery) of no more than 2.5 mCi of the radiotracer [18F]MeFWAY, as per RDRC protocol.

Simultaneous MRI Scan: An MRI scan will be performed simultaneously with the PET scan. Participants will receive an array of structural and functional MRI scans (e.g. T1 and T2-weighted structural images,

IRB# 2012-1826-F
PI: [name]

Stony Brook University Human Subjects Committee (IRB)
PSF 2/23/15
Page 19 of 37

diffusion tensor imaging [DTI], pseudocontinuous arterial spin labeling [pCASL], etc.) The anatomical image (T1) will be used to localize anatomic regions of interest on the PET scan. During this time, subjects will be monitored by the MRI technician. During the rest of the PET acquisition, participants will receive an array of structural and functional MRI scans.

Structural scans may include:

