In the event that an arterial line cannot be placed, we will use the simultaneous estimation (SIME) approach as discussed in the PET scan procedure section. This involves drawing one 12 cc sample via an arterial stick at 50 min post-radioligand injection for DASB, and at the 60 min post-radioligand injection timepoint for CUMI. This approach reduces the risk and burden to patients as it does not involve placing an indwelling catheter, but rather drawing a single blood sample. If the SIME approach fails, we will only draw from the venous line at the 50 and 80 time points for DASB and the 60 and 90 min time points or CUMI as described in the PET scan section.

3. Blood sampling & IV line insertion

Drawing blood and inserting an intravenous line (IV) into an arm vein are safe and standard medical procedures. Sometimes a bruise will occur at the puncture site and rarely, a blood clot or infection will occur in the vein. Certain individuals may feel light-headed during venipuncture. The volume of blood collected during the PET scans, will be approximately 16 tablespoons at most. At screening, 15.2ml will be drawn. An additional 8.5ml of blood will be drawn weekly until Lithium levels are therapeutic. This is not expected to have any serious negative effects on a study participant.

The risks of bruising, clotting, and infection will be minimized by having venipuncture performed by trained and experienced personnel using aseptic technique. To avoid injury due to fainting, the antecubital vein catheter will be inserted when the subjects are recumbent. The blood draws during PET scanning sessions will be obtained from the already inserted catheter, to minimize discomfort.

For patients who have low hemoglobin levels, possible adverse effects of blood sampling will be minimized by using the SIME approach. No additional risks are introduced by the simultaneous estimation (SIME) approach.

4. Discomfort during scanning (PET and MRI)

It may be uncomfortable to lie motionless in the cameras (both PET and MRI) and it may cause some subjects to feel anxious. Our staff will be available to provide support, reduce anxiety, optimize the comfort of the subject and remove the subject from the machine if requested.

5. MRI/fMRI Scan

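### The stated 180 ml blood maximum for the CUMI-101 and DASB PET procedure conflicts with the protocol's own 120 cc DASB draw and does not match the 16 tablespoons in its risk text

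*Protocol*

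**What the plan says.** Four places in the protocol bear on the volume of blood drawn at PET.

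- **Section D.5, PET Studies, CUMI-101 scan:** "90 ml or less will be collected during scan time". DASB sampling is then to follow the same pattern, with no separate volume, and the paragraph ends with the total: "maximal blood sampling during the entire PET procedure will be approximately 180 ml (about 12 tablespoons".
- **Section D.5, PET Studies, low-hemoglobin paragraph:** this opens "In cases where the subject has a hemoglobin level less than 12 for males and less than 11 for females" and replaces the full draw with a single sample under the simultaneous estimation (SIME) approach. It describes the saving as one 12 cc sample "instead of 120 cc being drawn during the DASB scan".
- **Section G, item 3 (Blood sampling & IV line insertion):** the volume for the PET scans "will be approximately 16 tablespoons at most".
- **Section D.5, Alternate Location and Tracer for PET Scans:** for [18F]MeFWAY, "120 mL or less (about 4 ounces or 1/2 cup) will be collected during each scan".

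Smaller draws are listed separately in PET Studies. One is taken before injection: "Before injection of the radiotracer, approximately 8ml of venous blood will be collected". One is for women only: "Approximately 8ml of blood will be drawn the day of the PET scans for female participants". In addition there are 4 mL venous samples at two times in each scan. The protocol does not say whether any of these count towards the totals.

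SIME sample times are given for DASB (50 min) and CUMI-101 (60 min) only.

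**The concern.** A stated maximum for blood drawn in a research procedure is a participant-safety figure. Staff work from the procedure text, and the risk text describes the burden to subjects. Here the lower total stands in the procedure text and the higher one in the risk text. A volume given for one of the two scans, in the same section as the lower total, does not fit that total. A scan team drawing 120 ml for DASB after 90 ml for CUMI-101 would follow both per-scan figures and still exceed the stated maximum for the procedure.

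**Working it through.** Inputs are the volumes listed above; 1 cc is taken as 1 ml.

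1. **Reproduce the stated total.** CUMI-101 90 ml + DASB 90 ml (implied by the instruction to sample in the same way) = 180 ml. The conversion is 180 / 12 = 15 ml per tablespoon. The paragraph is consistent within itself.

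2. **Use the stated DASB draw.** 90 + 120 = 210 ml; 210 / 15 = 14 tablespoons. Excess over the maximum: (210 − 180) / 180 = 16.7%. For 180 ml to hold with DASB at 120 ml, CUMI-101 could take at most 180 − 120 = 60 ml, whereas the protocol allows it 90 ml.

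3. **Convert the risk-text figure.** 16 × 15 = 240 ml. Excess over the maximum: (240 − 180) / 180 = 33.3%. At 14.787 ml per tablespoon the figure is 236.6 ml, so rounding of the unit does not explain the gap.

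4. **Test whether the small draws reconcile the figures.** Assume that none is already counted and that there are four 4 mL venous samples (two per scan).

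| Draws added | On 180 ml | On 210 ml |
|---|---|---|
| 8 ml pre-injection | 188 | 218 |
| + 8 ml hormone sample (women) | 196 | 226 |
| + 4 × 4 ml venous | 212 | 242 |
| with the pre-injection draw taken twice | 220 | 250 |

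From 180 ml the extras reach at most 220 ml, short of 240 ml. From 210 ml they can reach about 240 ml, which might explain the risk text, but 180 ml is then not a maximum.

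5. **Test a different scope for the risk text.** If it covered both the baseline and the repeat session, the procedure text would give 2 × 180 = 360 ml, not 240 ml. Two scans at 120 ml make 240 ml exactly; this could mean CUMI-101 and DASB at 120 ml each, or two MeFWAY scans. The protocol does not say which, if either, was meant.

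None of these readings lets the 180 ml maximum stand beside a 120 cc DASB draw and a 90 ml CUMI-101 cap.

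**The case against.** The best reply is that the conflict is narrower than it first looks, and much of that reply stands.

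- A reader might infer three competing ceilings for one session. Only two totals are printed, 180 ml and about 16 tablespoons. The 210 ml is a sum of two figures from different paragraphs.
- The risk text speaks of the PET scans in general. It names neither tracer nor session, in a protocol that also allows 120 mL per MeFWAY scan. A generous figure there errs on the cautious side. So the gap between 180 and 240 ml is a mismatch to be explained, not proof that the risk text is wrong.
- No volume limit is given that any of these totals would breach, and item 3 of Section G expects no serious effect from the sampling. The documents do not support a claim of harm.

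A reader might also infer that the protocol promises MeFWAY patients a one-sample protection that cannot be delivered. That goes too far. The low-hemoglobin rule in PET Studies and the failed-line text in Section G, item 2, both specify SIME for DASB and CUMI-101. Only the general low-hemoglobin sentence in item 3 names no tracer, and low hemoglobin is itself a listed exclusion, so few such patients are likely. What remains is an ambiguity: MeFWAY scans also use an arterial line, and the text does not say what happens if one cannot be placed.

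The objection leaves the DASB volume untouched: 90 ml by implication in one paragraph, 120 cc by statement in another.

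**Conclusion.** The protocol is inconsistent as written. The procedure maximum of about 180 ml rests on 90 ml for DASB, while the same section puts the full DASB draw at 120 cc. Taking the second figure, the maximum is understated by 30 ml (17%). The risk text is about 60 ml (33%) above it, on the assumptions that it describes the same two-scan procedure and uses the same 15 ml tablespoon. The documents do not show which DASB volume is correct.

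This is a correction to a safety figure in the operative text. It does not touch sample size, power or the planned analysis. The missing MeFWAY sample time is a secondary point of clarity only.

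**What to change.** Confirm the DASB draw from the blood-sampling schedule, then make PET Studies (both paragraphs) and Section G, item 3, agree.

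- **If DASB is 120 ml:** raise the procedure maximum to at least 210 ml (14 tablespoons) and match the risk text to it.
- **If DASB is 90 ml:** change the low-hemoglobin paragraph to 90 cc and the risk text to about 12 tablespoons.
- **In either case:** say whether the 8 ml pre-injection draw, the 8 ml hormone draw and the 4 ml venous samples are included. If they are not, set the ceiling to cover them.

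Separately, add a clause to the Alternate Location section and to Section G, items 2 and 3, saying whether the SIME fallback applies to [18F]MeFWAY and, if so, at what time point. I would not add a rule sending such patients to Yale for CUMI-101. MeFWAY is used when the patient cannot travel or Yale lacks capacity, so the rule would often be unworkable. It could also mix two tracers within one patient's pre/post pair.

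The cost is a check of the sampling schedule and a few sentences, with no change to the analysis.
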